10.2 Definitions

The following definitions apply:

Baseline - last observation collected prior to the date/time of study drug administration, unless otherwise noted.

Treatment group - each of the five BG00011 dose groups and the combined placebo group.

10.3 Demographics and Baseline Characteristics

Subject disposition will be summarized for the safety and efficacy populations. Reasons for discontinuation will be summarized by treatment group. The demographic variables age, sex, race, ethnicity, body weight, height, and body mass index will be summarized. By-subject listings of these variables will be provided.

Listings will also be created for subject eligibility, smoking history, and general/IPF-specific medical history.

10.4 Prior and Concomitant Medications

Prior and concomitant medications will be listed in the by-subject data listings. WHODRUG Version March 2011 or higher will be used to encode these medications.

10.5 Protocol Deviations

Protocol deviations will be listed.

10.6 Study Medication Administration

Study medication administration will be listed and the frequency of subjects who were administered treatment at each of the 8 visits will be summarized.

10.7 Pharmacokinetic Assessment

The date and time of pharmacokinetic (PK) blood sample collections by treatment group and by subject will be listed. The analysis of PK data will be described in a separate PK analysis plan and provided in a separate report.

10.8 Safety and Tolerability Assessments

Data will be summarized and presented by treatment group, defined as each of the BG00011 dose groups, the combined BG00011 group, and the combined placebo group. Data will be listed by treatment group. The safety population will be used for the following safety analyses. No inferential statistical analyses are planned.

10.8.1 Adverse Events

Adverse events (AEs) will be coded using the Medical Dictionary for Regulatory Activities (MedDRA Version 14.0 or later). Summary tables will be based on treatment emergent AEs (TEAE). A TEAE is defined as an AE that occurs during or after first dose or which is present prior to study drug administration and becomes more severe during or after first dose. Any event occurring prior to the first dose of study medication will be recorded as medical history. Related events are those classified as Possible, Probable, or Definite by the investigator. All AE analyses will be performed on TEAEs. All TEAEs will be listed by subject.

The following will be summarized and presented for each treatment group:

- The total number of TEAEs for each treatment group overall, by highest severity, by strongest causal relationship to study medication, the frequency of adverse events, the number of subjects with treatment emergent serious adverse events (TESAEs), and the number of subjects with TEAEs leading to study discontinuation;
- The number and percentage of subjects experiencing a TEAE for each system organ class (SOC) and each preferred term (PT) within each SOC;
- The number and percentage of subjects experiencing a TEAE for each preferred term (PT) in descending frequency;
- The number and percentage of subjects experiencing a TEAE by greatest severity for each system organ class (SOC) and each preferred term (PT) within each SOC;
- The number and percentage of subjects experiencing a related TEAE for each system organ class (SOC) and each preferred term (PT) within each SOC;
- A listing of subjects experiencing a TESAE;
- A listing of subjects experiencing a TEAE leading to withdrawal; and
- A listing of subject deaths occurring on study and relatedness to TEAE.

The incidence of TEAEs will be calculated by dividing the number of subjects who have experienced the event by the number of subjects in the treatment group. Thus, the incidence of TEAEs counts only the first occurrence of an event for each subject in that treatment group that experiences the event, and does not represent the total number of episodes of the particular event in the treatment group. If a subject has repeated episodes of a particular TEAE, only the most severe episode or the episode with the strongest causal relationship to study medication, as appropriate, will be counted.

A subject with more than one TEAE for a particular PT will be counted only once in the total of subjects experiencing TEAEs in that particular PT. Likewise, a subject with more than one type of TEAE in a particular SOC will be counted only once in the total of subjects experiencing

TEAEs in that particular SOC. Similarly, a subject who has experienced a TEAE in more than one SOC will be counted only once in the total number of subjects experiencing TEAEs in all SOCs.

All occurrences of all TEAEs will be listed for each subject. In the listing of individual subjects who have TEAEs, the following information on each episode will be provided: verbatim term, PT, SOC, severity of the event, relationship to study medication, onset date, resolution date, treatment given to treat the adverse event, the outcome, and whether the event was a TESAE.

A listing of any subject deaths occurring on study will be provided. Deaths on study are those which occur after randomization but prior to early discontinuation or completion of study.

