6. STUDY DESIGN

This is a multi-center, randomized, double-blind, placebo-controlled, multiple dose, dose-escalation study designed to evaluate the safety, tolerability, PK, immunogenicity, and impact on BAL and peripheral blood biomarkers of BG00011 activity in subjects with IPF conducted at approximately 15 centers in North America.

Approximately 40 subjects will be enrolled into 5 sequential ascending dose cohorts ([Table 1](#)). Cohorts will include 8 subjects randomized to receive either BG00011 (6 subjects) or placebo (2 subjects). Additional subjects may be enrolled if deemed appropriate by the Data Safety Monitoring Board (DSMB). Doses to be administered are as follows:

Table 1: Dosing Cohorts

Cohort	Dose	Number of Subjects	
		BG00011	Placebo
1	0.015 mg/kg	6	2
2	0.1 mg/kg	6	2
3	0.3 mg/kg	6	2
4	1.0 mg/kg	6	2
5	3.0 mg/kg	6	2
Total Number of Subjects		30	10

Subjects with clinical symptoms and features consistent with IPF prior to screening; forced vital capacity (FVC) \geq 50% of predicted value; carbon monoxide diffusion capacity, corrected for hemoglobin (DL_{CO}/Hb) \geq 30% of predicted value; oxygen (O₂) saturation $>$ 90% while breathing ambient air at rest or receiving \leq 2 L/minute of supplemental oxygen; residual volume (RV) \leq 120% of predicted value; a ratio of the forced expiratory volume in one second (FEV₁) to FVC \geq 0.65 after the use of a bronchodilator during screening pulmonary function tests (PFTs); high resolution computed tomography (HRCT) consistent with usual interstitial pneumonia (UIP) pattern; and who meet the other inclusion/exclusion (I/E) criteria are eligible to enroll in the study. Subjects who do not qualify for study eligibility may be rescreened at the discretion of the Principal Investigator.

Each subject within a dose cohort will be randomized to receive either BG00011 or placebo and will participate in 2 consecutive study periods: 1) each subject will receive 8 consecutive weekly doses of BG00011 (or placebo) (Period 1; Multiple Dose [MD] phase); and, 2) each subject will be monitored for 12 weeks (8 weeks for Cohorts 4 and 5) following administration of the last dose of study drug (Period 2; Follow-Up [FU] Phase).

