7. TREATMENT

BG00011 will be administered as an SC injection. Doses will be 0.015 mg/kg, 0.1 mg/kg, 0.3 mg/kg, 1.0 mg/kg, and 3.0 mg/kg. Weight obtained at initial screening will be used to calculate dose throughout the study. At the end of a screening period, eligible subjects will return for dosing on Day 1-MD. Study drug will be administered once weekly for 8 doses (7 weeks), i.e., on Days 1-MD, 8-MD, 15-MD, 22-MD, 29-MD, 36-MD, 43-MD, and 50-MD of the multiple-dose period.

In cohorts 1 to 3, each subject’s participation in the study will be for approximately 24 weeks (~5.5 months), i.e., up to 5 weeks to perform screening/entry evaluations, followed by 7 weeks of double-blind study dosing (8 doses) and a Follow-up period of 12 weeks. For Cohorts 4 and 5, the subject’s participation in the study will be for approximately 23 weeks (~5.5 months), i.e., up to 8 weeks to perform screening/entry evaluations, followed by 7 weeks of double-blind study dosing (8 doses) and Follow-up period of 8 weeks.

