10. STATISTICAL METHODOLOGY

10.1 General

Data listings will be provided by treatment group, subject and visit, if applicable. Summary statistics and statistical analyses will only be presented for data where detailed in this SAP. For continuous data, summary statistics will include the arithmetic mean, arithmetic standard deviation (SD), median, minimum (Min), maximum (Max) and n; for log-normal data the geometric mean and geometric coefficient of variation (CV) will also be presented. For categorical data, frequency count and percentages will be presented. Data listings will be provided for all subjects up to the point of withdrawal, with any subjects excluded from the relevant population highlighted. Summary statistics and statistical analyses will generally only be performed for subjects included in the relevant analysis population. For the calculation of summary statistics and statistical analysis, unrounded data will be used.

Due to the small number of subjects expected to enroll at each participating center, all summaries and analyses will be performed using data pooled across centers. Data for BG00011 treated subjects will be grouped by treatment group. Data for all placebo subjects, regardless of treatment group, will be treated as one group. Data will be summarized and presented by treatment group, defined as each of the BG00011 dose groups and the combined placebo group. Data will be listed by treatment group. Exposure to study medication will be tabulated by treatment group.

Mean change from baseline is the mean of all individual subject’s change from their baseline value. Each individual change from baseline will be calculated by subtracting the individual subject’s baseline value from the value at their subsequent visit(s). The individual subject’s change from baseline values will be used to calculate the mean change from baseline using a SAS[®] procedure such as Proc Univariate.

Data analyses will be performed using SAS[®] Version 9.1.3 or greater.

As previously stated (Section 4), this document describes the planned analyses for this Phase 2a study evaluating the safety, tolerability, PK, immunogenicity, and impact on BAL and peripheral blood biomarker of multiple doses of BG00011 in subjects with IPF. Some of the analyses described in this SAP will be performed by outside vendors. These data will be imported to the Biometrics database for study 203PF201 or, alternatively, provided as separate reports.

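### If adverse events are collected to the end of follow-up, the by-dose TEAE tables cover 19 planned weeks at the three lower doses, 15 at the two highest and a mean of 17.4 in pooled placebo

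*SAP*

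**What the plan says.** **Window and measure (SAP 10.8.1).** The window opens at first dose: "A TEAE is defined as an AE that occurs during or after first dose". A pre-existing event that worsens after first dose also counts. No closing day is given. Incidence is "calculated by dividing the number of subjects who have experienced the event by the number of subjects in the treatment group", and "the incidence of TEAEs counts only the first occurrence of an event for each subject in that treatment group". The first summary listed is a count of events, not of subjects: "The total number of TEAEs for each treatment group overall".

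**Follow-up (SAP 6 and 7).** Section 6 says that "each subject will be monitored for 12 weeks (8 weeks for Cohorts 4 and 5) following administration of the last dose of study drug". Section 7 repeats the shorter period for Cohorts 4 and 5: "followed by 7 weeks of double-blind study dosing (8 doses) and Follow-up period of 8 weeks". Dosing is eight weekly doses over 7 weeks in every cohort. Section 6.1 places Day 1-FU on the day of the last dose, Day 50-MD, so there is no gap between the periods.

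**Groups (SAP 10.1 and 10.8).** "Data for all placebo subjects, regardless of treatment group, will be treated as one group". Safety results are shown for "each of the BG00011 dose groups, the combined BG00011 group, and the combined placebo group".

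**The concern.** Safety and tolerability of escalating doses is the primary objective, and section 10.8 plans no inferential analysis. The descriptive tables by dose are therefore the main safety result, and a reader will look along the columns for a dose trend.

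The length of follow-up changes between 0.3 and 1.0 mg/kg. If adverse events are collected throughout follow-up, the columns for 1.0 and 3.0 mg/kg cover four planned weeks fewer than those for 0.015 to 0.3 mg/kg. The pooled placebo column mixes the two lengths. With equal underlying hazards, the two highest doses can then only look the same as the other columns or better, never worse. That is the less welcome direction in a dose-escalation safety study.

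The two measures are affected differently. Incidence loses only those subjects whose first occurrence falls in weeks 9 to 12 after the last dose. TEAE totals lose every event in those weeks.

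**Working it through.** **Inputs from the SAP.** Dosing 7 weeks in all cohorts (section 7). Follow-up 12 weeks in Cohorts 1-3 and 8 weeks in Cohorts 4-5 (sections 6 and 7). Six BG00011 and two placebo subjects per cohort (section 6, Table 1).

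**The plan's own figures.** Screening + dosing + follow-up is 5 + 7 + 12 = 24 weeks for Cohorts 1-3 and 8 + 7 + 8 = 23 weeks for Cohorts 4-5. Both match section 7. The totals look alike only because the longer screening in Cohorts 4-5 nearly offsets the shorter follow-up.

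**Planned weeks from first dose.**
- Cohorts 1-3: 7 + 12 = 19
- Cohorts 4-5: 7 + 8 = 15
- Pooled placebo: (6 × 19 + 4 × 15)/10 = 17.4
- Combined BG00011: (18 × 19 + 12 × 15)/30 = 17.4

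**Assumptions for size (not in the SAP).** Collection runs to the end of follow-up, and the hazard is equal in all groups. Incidence over 19 weeks is I. The hazard in the last four weeks is r times the earlier hazard, with r from 0 to 1. Then:
- λ = −ln(1 − I)/(15 + 4r)
- 15-week incidence p15 = 1 − exp(−15λ)
- pooled placebo incidence = 0.6 I + 0.4 p15
- gap to low dose = I − p15; gap to placebo = 0.6 (I − p15)
- events per subject, high dose relative to low dose = 15/(15 + 4r)
- events per subject, high dose relative to placebo = 15/(0.6(15 + 4r) + 0.4 × 15)

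Results for I = 25%:

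| r | Cohorts 4-5 | Placebo | Gap to low dose (points) | Gap to placebo (points) | Events per subject v low dose | Events per subject v placebo |
|---|---|---|---|---|---|---|
| 0 | 25.0% | 25.0% | 0 | 0 | 1.00 | 1.00 |
| 0.25 | 23.6% | 24.5% | 1.4 | 0.8 | 0.94 | 0.96 |
| 0.5 | 22.4% | 24.0% | 2.6 | 1.6 | 0.88 | 0.93 |
| 1 | 20.3% | 23.1% | 4.7 | 2.8 | 0.79 | 0.86 |

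In a group of six, the largest gaps in the table are 6 × 0.0468 = 0.28 subject against a low dose and 6 × 0.0281 = 0.17 subject against placebo.

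**Other incidences, constant hazard (r = 1).** I = 10% gives p15 = 8.0% and gaps of 2.0 and 1.2 points. I = 50% gives p15 = 42.1% and gaps of 7.9 and 4.7 points. With S = 1 − I, the gap S^(15/19) − S is largest at I = 67.5%: 8.7 points to a low dose and 0.6 × 8.7 = 5.2 to placebo, or 0.52 and 0.31 subject in six.

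**Scale.** At 25%, the standard error of a difference is √(0.1875 × (1/6 + 1/6)) = 25 points for 6 v 6 subjects and √(0.1875 × (1/6 + 1/10)) = 22 points for 6 v 10.

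**The case against.** The strongest objection is that everything depends on a collection period that the SAP does not give. A SAP may leave that period to the protocol, so its absence is no fault. Section 6 speaks of monitoring through follow-up, which supports collection to the end but does not prove it. Section 10.8.1 counts deaths up to completion of study, but that is a separate window, starting at randomization. If collection ends at one common interval of 8 weeks or less after the last dose, the imbalance disappears. This stands, and the point is conditional for that reason.

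Second, subjects with the event over subjects in the group is a conventional, clearly labelled proportion, and the differing follow-up is stated openly. That is correct: nothing here is false or contradictory. The weakness is that applying this measure to windows tied to dose makes the columns less comparable than they need be.

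Third, the shift is small beside sampling variation, and onset dates are listed for every TEAE, so late events could be found by hand. Both are true. They lower the severity, but the shift is systematic and easily removed.

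Fourth, exposure is tabulated (section 10.1) and discontinuations are summarised (section 10.3). These give context, but neither gives observation time.

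A reader might go further and infer that the overall drug-placebo safety comparison or the escalation decisions are biased. The SAP does not support that. Combined BG00011 and combined placebo have the same 60:40 mix and the same 17.4-week planned mean, and escalation rests on data through Day 15 (section 10.9).

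**Conclusion.** The point holds as a cheap improvement of low severity. It depends on adverse events being collected to the end of planned follow-up. On that condition, by-dose TEAE incidences and totals modestly under-count the two highest doses relative to the three lower doses and pooled placebo. At 25% incidence over 19 weeks the gap is 0 to 4.7 points against the low doses and 0 to 2.8 against placebo. Totals per subject at a high dose are 0.79 to 1.00 times those at a low dose. The upper ends need a hazard that stays constant until 12 weeks after the last dose. If events cluster around dosing, the effect approaches zero. A hazard that rose late would give more, but nothing in the SAP suggests one.

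Comparisons within Cohorts 1-3 and between Cohorts 4 and 5 are also unaffected. It would be wrong to read this as showing that the tables will hide a dose-related signal. The expected shift is about half a subject in six at most under a constant hazard, no test is planned, and the windows are planned ones that withdrawals or added subjects would alter.

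**What to change.** Before unblinding, add to section 10.8.1 a by-dose summary of TEAE incidence, TEAE totals and numbers of subjects with TESAEs, for onset from first dose through 56 days after each subject's last dose received. For subjects who complete dosing this is Day 57-FU (57 − 1 = 56 days after the last dose; 49 + 56 = 105 days, or 15 weeks, after the first). It lies within every cohort's planned follow-up, and section 10.8.11 already uses that day for Cohorts 4 and 5. Tying the cut-off to the last dose received also defines it for subjects who stop dosing early. Keep the full-period tables so that no late or serious event is lost, and add a row with each group's realised observation time.

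The cost is wording in the SAP and table shells, one date cut-off from onset dates already planned for listing, and one extra set of descriptive tables. The cut-off does not equalise early withdrawal from follow-up; the observation-time row is there to show it.

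If collection already ends at the same interval of 8 weeks or less after the last dose in every cohort, stating that in section 10.8.1 is enough and the extra tables are not needed.

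### The SAP's only death listing leaves out a known death that occurs after a subject has left the study early

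*SAP*

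**What the plan says.** SAP section 10.8.1 mentions a death listing twice. The bullet list of planned outputs asks for "A listing of subject deaths occurring on study and relatedness to TEAE". The closing paragraph of the section again promises a listing of deaths on study and then defines them: "Deaths on study are those which occur after randomization but prior to early discontinuation or completion of study".

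The same section handles adverse events differently. The TEAE window opens at first dose and has no stated end: "A TEAE is defined as an AE that occurs during or after first dose". The listing rule is "All occurrences of all TEAEs will be listed for each subject", and the details shown for each episode include "the outcome, and whether the event was a TESAE". Early exits because of adverse events are expected: the section counts "the number of subjects with TEAEs leading to study discontinuation" and asks for "A listing of subjects experiencing a TEAE leading to withdrawal".

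Section 10.1 has a general rule for all listings: "Data listings will be provided for all subjects up to the point of withdrawal". It makes no exception for adverse events or deaths.

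**The concern.** Safety and tolerability is the primary objective (SAP section 5). Dose groups have 6 BG00011 subjects each (section 6, Table 1) and no inferential safety analysis is planned (section 10.8), so readers will rely heavily on individual listings. The death listing is where they will look for deaths and their relation to adverse events.

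The definition of a death on study closes when the subject discontinues early. A subject who withdraws because of a TEAE and later dies of it is a clear candidate for a listing that must show the relation between death and TEAE. Under the rule as written, that subject has no entry, although the sponsor may hold the record. The other adverse event listings are then the only place to find the death, and the general sentence in section 10.1 leaves some doubt about whether they carry information from after withdrawal.

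**Working it through.** The SAP gives no figure that bears on this point, so the check sets its rules side by side.

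**Inputs**
- Death listing (10.8.1): opens at randomization, closes at early discontinuation or completion.
- TEAE listing (10.8.1): opens at first dose, no closing time; shows outcome and seriousness.
- Listing of TEAEs leading to withdrawal and listing of serious TEAEs (10.8.1): no closing time of their own.
- General rule for listings (10.1): up to the point of withdrawal.

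Early discontinuation is read here as leaving the study, in line with the phrase "the number of subjects with TEAEs leading to study discontinuation". If it meant stopping study drug, the exclusion would be wider.

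**Step 1: the death listing.** A death before early discontinuation is listed. A death after it fails the definition and is not listed, whatever its cause. No other output in the SAP is dedicated to deaths, so this exclusion follows from the definition alone and needs no other assumption.

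**Step 2: the other listings.** Take three kinds of death in a treated subject and ask where each appears.

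| Case | Death listing | AE listings if 10.8.1 governs | AE listings if the 10.1 cut were applied |
|---|---|---|---|
| Death before leaving the study | Yes | Yes | Yes |
| TEAE starts before withdrawal and causes it; death from it afterwards | No | Event and fatal outcome shown | Event shown, also as leading to withdrawal; later fatal outcome in doubt |
| New fatal event starts after withdrawal | No | Event and fatal outcome shown | Event may be absent |

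The first column of results is fixed by the definition. The last two differ only in whether information from after withdrawal is shown.

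**Step 3: which rule governs the AE listings.** Section 10.8.1 says twice that all TEAEs are listed, and it is the more specific text. Section 10.1 is general, but carries no qualifier, and neither section refers to the other. The natural reading is that 10.8.1 governs, but the SAP does not say so.

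**Step 4: size.** The SAP plans a listing of deaths and no death rate or summary table of deaths, so no summary changes. It gives no expected mortality or withdrawal rate, so the number of deaths affected cannot be calculated.

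**The case against.** The strongest case on the other side has four parts.

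- **The death is not hidden.** If a subject withdraws because of a TEAE and dies of it, that TEAE began before withdrawal. It appears in the TEAE listing and in the listing of TEAEs leading to withdrawal, and in the serious TEAE listing if it was already serious. This stands, and it is the main reason why the point is minor. It does not put the death in the death listing.
- **Sections 10.1 and 10.8.1 need not conflict.** The sentence in 10.1 goes on to say that subjects excluded from the relevant population are highlighted. It can fairly be read as saying that withdrawn and excluded subjects stay in the listings. The specific rule in 10.8.1 would then prevail. This largely stands. A reader might infer that the SAP cuts AE data at withdrawal, or that its two rules are in open contradiction. The text does not support either; it only leaves the precedence unstated.
- **The data may not exist.** Whether deaths are collected after a subject leaves is a protocol matter, and the protocol is not at hand. The TFL shells mentioned in section 4 are not shown either. This limits the point to deaths that are recorded. It does not explain why a recorded death should be left out.
- **Serious events reach the DSMB throughout the study (section 10.9).** This is true, but it concerns oversight during the trial and not the listings in the study report.

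A reader might also try to size the gap as the part of the 12-week (8-week in Cohorts 4 and 5) follow-up that remains when a subject leaves. The SAP does not support such a figure. Section 6 describes follow-up after eight weekly doses, section 6.1 ties its first day to Day 50-MD, and nothing says that the window applies to subjects who leave early. Any number would rest on an assumed day of exit.

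**Conclusion.** The point holds for the death listing: by its own definition, the SAP's only death listing omits a known death after early discontinuation, even one that follows from the TEAE that led to withdrawal. For the AE listings the risk is conditional. A fatal outcome reached, or a new fatal event starting, after withdrawal could be lost only if the general sentence in 10.1 were applied to AE data.

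The size is small. At stake is an entry in one listing and, under the less natural reading, an outcome or event in others. No summary table or rate changes. The conclusion assumes that the death is recorded and that early discontinuation means leaving the study. It makes no claim that such deaths are likely, or that deaths long after completion ought to have been collected. Severity: minor.

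**What to change.** In section 10.8.1, replace the definition of deaths on study with a rule that lists every death after randomization recorded in the study or safety database, including deaths after early discontinuation. For each death show days since first dose, days since last dose, a flag for before or after discontinuation, and the associated TEAE, if any.

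In section 10.1, add that the AE, SAE and death listings follow section 10.8.1 and are not cut at withdrawal.

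The cost is wording in two sections and a few columns in one listing. No new data collection is needed, because only deaths already recorded are shown. The small downside is that a listed death may be remote from treatment; the timing columns and the flag let the reader see that.
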